4	Informational Contacts	[REDACTED], MD Senior Vice President/Drug Safety Risk Management InterMune, Inc. [REDACTED], MD Medical Advisor & Advisory Board Member NDA Regulatory Science Ltd. EU QPPV for InterMune, Inc.	[REDACTED], MD Medical Monitor for Roche [REDACTED] [REDACTED], MD EU OPPV for Roche [REDACTED]
6	List of Abbreviations	HLT, ICH, LFT, and NRP removed because they were not used in the protocol	PASS, Post-Authorisation Safety Study, was added.
8	Synopsis		ADDED: Protocol Number: WB29908 (InterMune PIPF-25)
8	Synopsis	Study Title	Protocol Title
8	Synopsis- Study Title	Post-Authorisations Safety Study (PASS) of Esbriet....	Post-Authorisation Safety Study of Esbriet....
8	Synopsis – Number of Registry Centres:	Up to 100...	Approximately 100...
12	Table 1: Table Header, column 3		ADDED: ± 4 weeks
12	Table 1: Row 15	0-----X	Information about and date of last Esbriet dose
12	Table 1: Row 16	0-----X	assessed throughout study
12	Table 1: Row 17	0-----X	assessed throughout study
12	Table 1: Row 18	0-----X	collected when associated with SADR or ADR of special interest

Page in Protocol with A3: 25 Apr 2014	Topic	Previously Read	Now Reads
12	Table 1: Row 19	0-----X	collected as patient completes study or withdraws before completing study
15	5.6 Patient Reconsent		ADDED NEW SECTION. (all subsequent sections are renumbered) All patients who are actively participating in the study will be asked to give verbal and written consent again, when the protocol is amended and changes are substantial (e.g., any change that impacts patient safety or the integrity of data). The informed consent will be updated to reflect the protocol changes. Patients who have discontinued will not be required to reconsent but they will be sent a letter from their study site to inform them of protocol or sponsor changes that could be relevant (e.g., a change of study sponsor/MAH or identification of a new, significant drug-related risk).
16	6.2 Follow-up: Years 1 and 2	The physician or other trained site staff will collect data via structured questionnaires administered to the patient during routine clinical visits.	The physician or other trained site staff will collect data from the patient during routine clinical visits.
20	8.1 Schedule of Assessments	The currently authorised SPC for Esbriet [®] recommends liver function test (LFT) monitoring every month for the first 6 months of Esbriet [®] therapy and every 3 months thereafter.	The currently authorised SPC for Esbriet recommends liver function test monitoring prior to beginning Esbriet, every month for the first 6 months of Esbriet therapy, and every 3 months thereafter.
21, 22	9.2.1 and 9.2.3		DELETED: high level term (HLT)
22	9.2.2. Baseline Assessment	Comparative demographic and baseline data will be summarized by treatments for IPF.	DELETED
22	9.2.3. Primary Analyses	Comparative safety data will be summarized by treatments for IPF.	DELETED

Page in Protocol with A3: 25 Apr 2014	Topic	Previously Read	Now Reads
22	9.3. Missing Data	As explained in the ICFs, reasonable attempts will be made to contact patients to limit missing data.	Reasonable attempts will be made to contact patients who discontinue the study or who are lost to follow-up.
23	10.1.2. Opinion of External Experts and Scientific Advisory Boards	The SAB will meet and review the registry data regularly and will make recommendations to the MAH.	The SAB will meet and review the registry data regularly and may make recommendations to the MAH about study conduct or data collection.
25	11.3. Patient Files	...5 years after completion of the registry.	...15 years after completion of the registry.
GLOBAL CHANGES			
Location	Action	Previously Read	Now Reads
Header	changed	InterMune UK Ltd. Protocol PIPF-025: 02 Dec 2010 Pirfenidone Protocol Amendment 1.0: 31 May 2012 Protocol Amendment 2.0: 10 Oct 2012 Protocol Amendment 3.0: 25 Apr 2014	Roche Registration, Ltd. Pirfenidone Protocol WB29908 InterMune Protocol PIPF-025
text	changed	any statement referring to treatment of “2 years”	to “up to 2 years”
text	changed	from “certain” European Union Member States	to “selected”
text	changed	follow up	follow-up
text	changed	re-consent	reconsent

LIST OF ACRONYMS AND ABBREVIATIONS

ADR	Adverse Drug Reaction
CHMP	Committee for Medicinal Products for Human Use
CRF	Case Report Form
CRO	Clinical Research Organization
eCRF	Electronic Case Report Form
EDC	Electronic Data Capture
EMA	European Medicines Agency
EU	European Union
GPP	Good Pharmacoepidemiology Practices
ICF	Informed Consent Forms
IEC	Independent Ethics Committee
IPF	Idiopathic Pulmonary Fibrosis
ISPE	International Society for Pharmacoepidemiology
MAH	Marketing Authorisation Holder
MedDRA	Medical Dictionary for Regulatory Activities
PASS	Post-Authorisation Safety Study
PT	Preferred Term
SAB	Scientific Advisory Board
SADR	Serious Adverse Drug Reaction
SAP	Statistical Analysis Plan
SOC	System Organ Class
SPC	Summary of Product Characteristics

1. SYNOPSIS

Protocol Number: WB29908 (InterMune PIPF-025)	
Protocol Title: Post-Authorisation Safety Study of Esbriet [®] (Pirfenidone): A Prospective Observational Registry to Evaluate Long-Term Safety in a Real-World Setting	
Condition/Disease: Idiopathic Pulmonary Fibrosis	
Number of Patients with IPF: 1000	Number of Registry Centres: Approximately 100 in selected EU Member States
Duration of Patient Participation: 2 years	Duration of Registry: 4 years
Background and Rationale: Idiopathic pulmonary fibrosis (IPF) is a progressive illness with an extremely poor prognosis; median survival after diagnosis is 2-5 years. Esbriet [®] is an orally bioavailable small synthetic non-peptide molecule that attenuates fibroblast proliferation, production of fibrosis-associated proteins and cytokines, and the increased biosynthesis and accumulation of extracellular matrix in response to cytokine growth factors such as transforming growth factor-beta and platelet-derived growth factor. Esbriet is authorised for the treatment of mild to moderate IPF. Although data from the development programme including Phase 3 trials demonstrate that Esbriet has an acceptable risk benefit profile in the treatment of mild to moderate IPF, there is a need, in real-world clinical practice, to establish the long-term safety profile of Esbriet treatment.	
Objective: The objective of this study is to evaluate the long-term safety profile of Esbriet in patients with IPF and to monitor for any unknown or potential risks of treatment with Esbriet.	
Design: This product registry is a multicentre, long-term, prospective, observational study to evaluate the long-term safety of Esbriet in patients with IPF. Patients will receive Esbriet at the discretion of their physicians and will be followed through the registry for up to 2 years after they begin treatment with Esbriet. This registry complies with the requirement of a post-authorisation safety study (PASS) and is a post-authorisation commitment, which has been approved by the Committee for Medicinal Products for Human Use (CHMP) at the European Medicines Agency (EMA).	
Registry Settings: The registry will initially enrol patients from approximately 100 pulmonary clinics throughout selected European Union (EU) Member States and is open to all patients who will receive Esbriet as part of normal clinical practice. The enrolment will be stopped when 1000 patients	

with a diagnosis of IPF have been enrolled. It is estimated that the enrolment will be completed within approximately 24 months. The Marketing Authorisation Holder (MAH) will closely monitor enrolment and will keep the Rapporteur and Co-Rapporteur informed of progress with the registry at regular intervals. If progress is not satisfactory, then the MAH will discuss with the Rapporteur and Co-Rapporteur any contingency that might be considered in order to increase the recruitment level in the context of the overall usage of the product within the EU. These may include, but are not limited to, extending the registry into another Member State, opening up more sites and intensifying the communication plan.

Each patient will be followed for up to 2 years. The MAH will also closely monitor the retention of patients and will undertake all reasonable efforts and methods to minimize loss to follow-up for the entire 2 years of observation.

Treating physicians will collect pre-specified data at baseline and approximately every 3 months thereafter for the duration of the study. In the event that a patient discontinues Esbriet treatment, all serious adverse drug reactions (SADRs), and adverse drug reactions (ADRs) of special interest will be collected until 28 days after the last dose of Esbriet.

Treatment:

The registry is observational; therefore, all treatment decisions are at the discretion of the patient's health care provider and are not mandated by study design or protocol. Cooperation of health care professionals is based on goodwill and no contractual sanctions will be applied by the MAH.

Inclusion Criteria:

- A clinical decision has been made, prior to study enrolment, to prescribe Esbriet
- Patients who are newly prescribed Esbriet therapy
- Initiation of Esbriet therapy is not more than 30 days prior to study enrolment
- Patient or legal representative provides informed consent and/or informed assent according to local regulations

Esbriet is only indicated for the treatment of mild to moderate idiopathic pulmonary fibrosis in adults. The registry protocol does not encourage use of Esbriet for other conditions or in paediatric patients. However, if a physician, in collaboration with the patient and/or legal representative, makes an independent clinical decision to prescribe Esbriet outside the terms of the Summary of Product Characteristics (SPC), those patients may be included in the registry.

Exclusion Criteria:

- Patients receiving an investigational agent defined as any drug that has not been approved for marketing for any indication in the country of the participating site
- Patient has received Esbriet therapy 31 days or more prior to current treatment course (e.g., prior participation in clinical trials)

- Patient has any contraindication for the use of Esbriet, according to the current local version of the SPC
- Patient or legal representative refuses to provide informed consent and/or informed assent according to local regulations

Data Collection (please see [Table 1](#)):

- Baseline data collection:
 - Demographics
 - Medical history
 - Concurrent diseases
 - IPF history
 - Prior and concomitant treatments for IPF
 - Concomitant treatment with warfarin
 - Reason/indication for Esbriet therapy (other than IPF)
 - Initial prescribed dose of Esbriet
 - Other (concomitant medications, height, weight, liver function tests)
- Follow-up data collection:
 - Serious adverse drug reactions
 - Clinically significant ADRs of special interest: These ADRs of special interest encompass all “important identified risks” and “important potential risks” as defined in the Esbriet Risk Management Plan and include:
 - Photosensitivity reactions and skin rashes
 - Abnormal liver function tests
 - Dizziness
 - Weight loss
 - Gastrointestinal symptoms
 - Fatigue
 - Falls
 - Drug interactions (including smoking)
 - Increased platelet counts
 - Specific cardiac events: supraventricular tachyarrhythmia, atrioventricular block/sick sinus syndrome, ventricular arrhythmia, bundle branch block, aortic or

pulmonic valvular incompetence

- Blood dyscrasias: agranulocytosis, leukopenia, neutropenia
- Angioedema
- Any other clinically significant ADRs based on the judgment of the prescriber
- Relevant laboratory and clinical tests, Esbriet dose, and concomitant medications for reported ADRs
- Esbriet dose changes or discontinuation and reasons for change/discontinuation
- Concomitant treatments for IPF
- Concomitant treatment with warfarin
- Patient registry withdrawals

Statistical Considerations:

No formal hypotheses will be tested. The study population for analysis of safety will include any patient who receives at least one dose of Esbriet regardless of the length of follow-up for that patient. Descriptive analyses will include frequency and measures of central tendency, range, and dispersion of clinical characteristics of the study population. Frequencies and cumulative incidence of reported ADRs will be summarized.

Ethical Considerations:

The registry will be conducted in accordance with the ethical principles that have their origins in the Declaration of Helsinki,¹ applicable privacy laws, and local regulations for each participating site. This non-interventional study will be conducted in accordance with the Guidelines for Good Pharmacoepidemiology Practices (GPP)² issued by the International Society for Pharmacoepidemiology (ISPE). When applicable, an independent ethics committee (IEC) will review and approve the protocol before any patient is enrolled. Appropriate informed consent and paediatric assent will be obtained from participating patients or their parents or legal representatives, if applicable.

Table 1: Registry Schedule of Assessments

Data Collected	Baseline	Follow-up visits (every 3 months ± 4 weeks)
Visit ID	1	2-9
Informed consent	X	-
Patient/legal representative and secondary contact information	X	X
Primary health care provider information	X	X
Demographics [age, gender, race/ethnicity (where allowed by local regulation), smoking history, alcohol use]	X	-
Medical history	X	-
Concurrent diseases	X	-
IPF history (date of diagnosis/duration of disease, method of diagnosis, pulmonary function at initiation of Esbriet®, oxygen supplementation)	X	-
Prior and concomitant treatments for IPF	X	X
Reason for Esbriet therapy (other than IPF)	X	-
Prescribed Esbriet treatment (initial dose, dose changes/discontinuation, reason for change/discontinuation)	X	X
Other (concomitant medications, height, weight, liver function tests)	X	-
Warfarin treatment	X	X
Esbriet discontinuation	information about and date of last Esbriet dose	
SADRs ^a	assessed throughout study	
ADRs of special interest ^a	assessed throughout study	
Relevant laboratory and clinical tests, Esbriet dose, and concomitant medications corresponding to reported ADRs	collected when associated with SADR or ADR of special interest	
Patient withdrawal from the registry ^b	collected as patient completes study or withdraws before completing study	

^a Patients will be interviewed at the specified time points to determine if any of these events have occurred since the last evaluation. However, the study physicians may report an event between evaluations if they become aware that such an event has occurred.

^b Patients may withdraw from the registry at any time following enrolment.

2. BACKGROUND AND RATIONALE

Idiopathic pulmonary fibrosis (IPF) is characterized by shortness of breath and typical histologic findings of interstitial fibrosis, inflammatory infiltrate, and destruction of normal lung architecture, collectively termed usual interstitial pneumonia. This progressive illness has a very poor prognosis with median survival after diagnosis ranging from 2-5 years.^{3,4}

Esbriet[®] is an orally bioavailable small synthetic non-peptide molecule that attenuates fibroblast proliferation, production of fibrosis-associated proteins and cytokines, and the increased biosynthesis and accumulation of extracellular matrix in response to cytokine growth factors, such as transforming growth factor-beta and platelet-derived growth factor. Esbriet is authorised for the treatment of mild to moderate IPF in adults. Although data from the development programme including Phase 3 trials demonstrate that Esbriet has an acceptable risk benefit profile in the treatment of mild to moderate IPF, there is a need, in real-world clinical practice, to establish the long-term safety profile of Esbriet treatment. The recommended dosage is 2403 mg/d given orally as three 267-mg capsules 3 times daily, after a 14-day dose escalation period.

In view of the recognised limitations of spontaneous reporting and the need to better define the long-term safety profile of Esbriet, as well as to monitor any unknown and potential risks, the Marketing Authorisation Holder (MAH) is conducting a Post-Authorisation Safety Study (PASS) in the form of an observational registry that will permit organised, prospective data collection to conduct pre-specified analyses. This multicentre, long-term, prospective study will collect data about the long-term safety profile of Esbriet. The design of this PASS registry is consistent with the principles of a non-interventional PASS as described in Volume 9A of The Rules Governing Medicinal Products in the European Union, Guidelines on Pharmacovigilance for Medicinal Products for Human Use, Part 1, Section 7.⁵

3. OBJECTIVE

The objective of this study is to evaluate the long-term safety profile of Esbriet in patients with IPF and to monitor for any unknown or potential risks of treatment with Esbriet.

4. REGISTRY DESIGN AND SETTING

4.1. Design

This product registry is a multicentre, long-term, prospective, observational study to evaluate the long-term safety profile as well as to monitor for any unknown or potential risks of treatment with Esbriet. Patients will receive Esbriet at the discretion of their physicians and will be followed through the registry for up to 2 years after they begin treatment with Esbriet. This registry constitutes a PASS and is a post-authorisation commitment, which has been approved by the Committee for Medicinal Products for Human Use (CHMP) of the European Medicines

Agency (EMA). The registry will be set up, conducted, and closely monitored by the MAH, or a designee with oversight by a project specific Scientific Advisory Board (SAB).

4.2. Setting

The registry aims to initially enrol patients from approximately 100 pulmonary clinics throughout selected EU Member States and is open to all patients who will receive Esbriet. Enrolment will stop when 1,000 patients with a diagnosis of IPF have been enrolled. It is estimated that the enrolment will be completed within approximately 24 months. The MAH will closely monitor enrolment and will keep the Rapporteur and Co-Rapporteur informed of progress with the registry at regular intervals. If progress is not satisfactory, then the MAH will discuss with the Rapporteur and Co-Rapporteur any contingency that might be considered in order to increase the recruitment level in the context of the overall usage of the product within the EU. These may include, but are not limited to, extending the registry into another Member State, opening up more sites and intensifying the communication plan.

Each patient will be followed for up to 2 years. The MAH will also closely monitor the retention of patients and will undertake all reasonable efforts and methods to minimize loss to follow-up for the entire duration of the registry. Treating physicians will collect pre-specified data at the baseline and every 3 months thereafter, for the duration of the patients' participation in study.

5. SELECTION AND ENROLMENT OF PARTICIPANTS

When applicable, an independent ethics committee (IEC) must approve the protocol and informed consent forms (ICF) prior to patient enrolment. Each patient or legal representative must participate in the informed consent process and sign the ICF for this protocol before data collection is initiated. The registry requires that documentation of informed consent is recorded in the source document for each patient.

5.1. Inclusion Criteria

Patients must meet all of the following criteria to be eligible for registry enrolment:

- A clinical decision has been made, prior to enrolment, to prescribe Esbriet; and
- Patient is newly prescribed Esbriet® therapy; and
- Initiation of Esbriet® therapy is not more than 30 days prior to study enrolment; and
- Patient or legal representative provides informed consent and/or informed assent according to local regulations

Esbriet is only indicated for the treatment of mild to moderate IPF in adults. The registry protocol will not encourage use of Esbriet for other conditions or in paediatric patients. However, if a physician, in collaboration with the patient and/or legal representative, makes an independent clinical decision to prescribe Esbriet outside the terms of the Summary of Product Characteristics (SPC), those patients may be included in the registry.

5.2. Exclusion Criteria

Patients are not eligible for this registry if they meet any of the following criteria:

- Patients receiving an investigational agent defined as any drug that has not been approved for marketing for any indication in the country of the participating site
- Patient has received Esbriet therapy 31 days or more prior to current treatment course (e.g., prior participation in clinical trials)
- Patient has any contraindication for the use of Esbriet, according to the current local version of the SPC
- Patient or legal representative refuses to provide informed consent and/or informed assent according to local regulations

5.3. Registry Enrolment

The registry initially aims to enrol patients from approximately 100 pulmonary clinics throughout selected EU Member States.

5.4. Physician Enrolment

The study will recruit pulmonologists and other physicians within the selected EU Member States who are likely to treat patients eligible for the registry.

5.5. Patient Enrolment

All patients undergoing treatment at any of the registry sites who meet the inclusion and exclusion criteria detailed above ([Section 5.1](#) and [Section 5.2](#)) may be included in the registry. Patients who are enrolled in the registry in anticipation of Esbriet use, but are not treated with Esbriet within 6 months of enrolment will be considered screen failures and will require re-consent for enrolment at a later date.

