9.2. Data Analyses

9.2.1. General Considerations

A detailed Statistical Analysis Plan (SAP) will be prepared and approved by the MAH prior to implementation. All SADRs, and ADRs of special interest will be recorded and coded using Medical Dictionary for Regulatory Activities (MedDRA) terms and presented by system organ class (SOC) and preferred term (PT). Anonymised characteristics of patients who are screened

for enrolment, but do not participate in the study, will be collected in screening logs and reviewed on an ongoing basis for the purposes of understanding enrolment trends.

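### Eligible new starters need not all be offered enrolment, and entry may follow first dose by up to 30 days, so incidence of early-onset ADRs can depend on early tolerability

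*Protocol*

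**What the plan says.** Section 5.5 (Patient Enrolment) states that patients treated at a registry site who meet the entry criteria "may be included in the registry". Section 4.2 (Setting) says the registry "is open to all patients who will receive Esbriet". Neither sentence obliges a site to approach each new starter.

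Section 5.1 sets the latest entry point: initiation of Esbriet "therapy is not more than 30 days prior to study enrolment". Entry before treatment is also foreseen. Section 5.5 has a rule for "Patients who are enrolled in the registry in anticipation of Esbriet use, but are not treated with Esbriet within 6 months of enrolment", who become screen failures. The registry can thus contain both patients enrolled before first dose and patients enrolled up to 30 days after it.

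Section 5 requires each patient or representative to "sign the ICF for this protocol before data collection is initiated", so a starter who never consents contributes no registry data. For people screened who do not take part, section 9.2.1 provides for anonymised characteristics in screening logs, "reviewed on an ongoing basis for the purposes of understanding enrolment trends".

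Section 9.2.3 defines cumulative incidence as patients with the event divided by patients enrolled. Section 9.1 justifies the sample size of 1,000 by precision alone.

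**The concern.** Section 2 describes a 14-day dose escalation, which lies wholly inside the 30-day entry window. By the time a late entrant is invited or consents, the site and the patient may already know how the drug was tolerated. A patient who started, reacted and stopped within that window still meets section 5.1. However, nothing directs the site to approach that patient, and section 5.5 describes candidates as people undergoing treatment.

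If such patients are approached or consent less often than others, they are lost from both the numerator and the denominator of section 9.2.3. The resulting error does not shrink as the sample grows, and the half-widths in Table 2 do not include it. What is at stake is the incidence of ADRs that appear in the first weeks, which the registry is meant to estimate in ordinary practice.

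**Working it through.** **1. The plan's own figure.** Table 2 gives the half-width of a normal-approximation 95% interval with n = 1,000: 1.96 × √(p(1 − p)/1000).

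- p = 2.5%: 0.968 points (stated 0.97).
- p = 10%: 1.859 points (stated 1.86).
- The other six rows also agree to two decimals.
- p = 22%, the top of the range quoted in section 9.1, has no row in the table; the same formula gives 2.57 points.

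**2. Effect of selective entry.** Let p be the true incidence among all eligible starters and f the share of would-be cases never enrolled, with non-cases all enrolled. Then

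observed incidence = p(1 − f) / (1 − pf).

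The protocol gives neither the timing of ADR onset nor a participation rate, so f is an assumption, varied here from 5% to 30%. Example: of 1,000 starters with p = 10% there are 100 cases; with f = 20%, 20 are missed, and 80/980 = 8.16%.

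| True p | f = 5% | f = 10% | f = 20% | f = 30% | Half-width (points) |
|---|---|---|---|---|---|
| 2.5% | 2.38% | 2.26% | 2.01% | 1.76% | 0.97 |
| 10% | 9.55% | 9.09% | 8.16% | 7.22% | 1.86 |
| 22% | 21.13% | 20.25% | 18.41% | 16.49% | 2.57 |

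Over this range the shortfall is 0.12 to 0.74 points for a 2.5% ADR, 0.45 to 2.78 for a 10% ADR and 0.87 to 5.51 for a 22% ADR.

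**3. Omission at which bias equals the half-width h.** Setting p − p(1 − f)/(1 − pf) = h gives f = h / [p(1 − p + h)].

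- p = 2.5%: f ≈ 39%, about 10 patients omitted per 1,000 enrolled.
- p = 10%: f ≈ 20%, about 21 per 1,000.
- p = 22%: f ≈ 14.5%, about 33 per 1,000.

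Common ADRs are therefore the more exposed. Since f counts only cases arising before a late entry, a low-frequency or late-onset ADR could hardly reach these values.

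**4. Direction.** The sign depends on who is left out. If instead a share g of non-cases were missed and all cases enrolled, observed incidence = p / [p + (1 − p)(1 − g)]. With p = 10% and g = 10% (again an assumption), 0.10/(0.10 + 0.81) = 10.99%, an upward error.

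**5. What the data can show.** Consent date is collected (section 6.1), and first-dose date is needed for time at risk (section 9.2.3). Each patient can therefore be classed as enrolled on or before first dose, or after it. Only the second group is open to this selection.

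**The case against.** The strongest reply is that section 5.5 is ordinary eligibility wording for a consent-based registry and that section 4.2 opens the registry to all. A reader might infer from the word 'may' that sites are entitled to pick among eligible patients. No section says so, and enrolment procedures are left to site training (section 11.1), which is not shown. What stands is narrower: no duty to offer is stated, so selection is possible under the text.

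A reader might also treat the 30-day window as a fault in itself. With the prior-exposure exclusion in section 5.2, it works as a new-user restriction that keeps out longer-term tolerant users, and section 5.5 provides for entry before first dose.

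It is tempting to say that no analysis could reveal the problem. That goes too far. The comparison in step 5 can look for it, though it cannot recover missing patients, and it belongs as naturally in the SAP as here, so its absence from the protocol is not held against the plan. The screening logs are also a partial safeguard: their stated purpose does not rule out looking at who was not enrolled. Their limit is that they cover only people who were screened, and the protocol names neither early stopping nor reason for non-enrolment as content.

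Finally, the objective is long-term safety (section 3), and a patient with an early ADR may remain on treatment and enrol. Both points limit the reach of the concern without removing it.

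**Conclusion.** The concern holds in a limited form. Sections 5.1 and 5.5 together let enrolment depend on early tolerability for patients who enter after first dose, and the denominator in section 9.2.3 carries any such selection into cumulative incidence. Patients enrolled before first dose are unaffected, and mainly early-onset ADRs are at risk.

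The size is unknown. Under assumed omission of 5% to 30% of would-be cases, a 10% ADR would be observed as 9.55% to 7.22%, a shortfall of about a quarter (0.45/1.86) to one and a half times (2.78/1.86) the stated half-width. A reader might infer that the registry's incidences are biased low by about its precision. The documents do not support that: it needs f near 20% for a 10% ADR, nothing in the protocol fixes f, and the sign reverses if patients with ADRs are preferentially enrolled. This is an inexpensive improvement to the design, not an error that invalidates the long-term results.

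**What to change.** - Amend section 5.5 so that sites offer enrolment to every consecutive eligible new starter, at the time of prescription where possible, including those who have already stopped Esbriet within the 30-day window.
- Add reason for non-enrolment to the existing screening log and, where local rules allow it to be recorded anonymously, whether Esbriet had already been stopped. This must stay within the consent requirement of section 5, so dated treatment details of people who have not consented should not be assumed available.
- Report the participation proportion.
- Compare early ADR incidence, over the same interval from first dose, between patients enrolled on or before first dose and those enrolled after it. The groups may differ for other reasons, so this is a check and not a correction. It also presupposes that ADRs between first dose and enrolment are recorded; section 7.2 says collection starts at first dose while section 7.3 refers to enrolment, and the two should be reconciled.

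Cost: one changed sentence with matching site training, one or two log fields, slightly more site effort and one added table. Extra log content may need ethics committee review. Because cooperation rests on goodwill without sanctions (Synopsis, Treatment), the offer rule cannot be strictly enforced, and patient refusal remains.
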